Arm: The different groups of the intervention. In this study, Arm 1 is the health promotion attention control and Arm 2 is the MBSR. Participants at a given site are assigned to one Arm or the other, by cohort).

Cohort: The group of people that are doing the interventions at the same time.

Cortisol: The body's main stress hormone, triggered by the adrenal glands. Cortisol is a glucocorticoid and is released in the body about 20 minutes after a stressor. The immediate stress response hormones (adrenaline and epinephrine) are released within seconds or minutes; if the brain continues to perceive something as stressful, then cortisol is released.

C-Reactive Protein (CRP): This is a protein made in the liver. CRP tends to increase when there is inflammation occurring in the body, (Lindqvist et al., 2014, 2017) induced by proinflammatory cytokines in the liver (Eklund, 2009). These heightened inflammatory responses can lead to health impairments including atherosclerosis (Wong et al., 2012) and cardiovascular disease (Coughlin, 2011) compounding health disparities in disadvantaged populations; CRP, in particular, has been linked with obesity (Visser et al., 2011) metabolic syndrome (Ridker et al., 2003) and CVD.(Ridker et al., 1998) Thus CRP can be used as marker for general inflammation and risk for inflammatory-related problems.

Other acronyms used in this protocol:

IISBR - Institute for Interdisciplinary Salivary Bioscience Research - https://iisbr.uci.edu/

- IISBR is a shared resource and scientific hub; researchers can gain practical experience/knowledge in salivary bioscience through the training programs (e.g., Spit

Camp). IISBR also provides the storage and analyses of the salivary samples collected in this study.

SECTION 1B. INTRODUCTION TO PTSD AND MBSR

Subsection 1B.1 - PTSD Basics

PTSD Diagnosis

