- Team Management of Biospecimen Collection Refusal
- Dealing with Program Attrition

Subsection 2.8 - Phase II Pre-intervention Assessments

After Informed Consent, participants will complete a series of self-report measures. These measures will be administered by Research Staff at a private location at the site. Responses options to each question will be provided to the participant, organized in a clearly labeled binder. The Research Staff will display the response options for each measure, read the options out loud, and then record the response on the tablet. At the end of each measure, the RA will "lock" the measure. There will be a prompt if any items have been missed. Please check that there is no missing data. The participant may take a break at any time. However, the participant should refrain from eating, drinking (except for water ~ 10 minutes prior to stress task), or smoking until after the second saliva collection to ensure the accuracy of the saliva sample.

Order of assessments

- 1. Drug test (urine)
- 2. TCU Drug Screen (self-report)
- 3. Self-compassion scale short form
- 4. General self-efficacy scale
- 5. Mindful Attention Awareness Scale
- 6. Difficulties I Emotion Regulation Scale
- 7. Satisfaction with Life Scale
- 8. Quality of Life Enjoyment and Satisfaction Questionnaire
- 9. MOS Social Support
- 10. Perceived Stress Scale
- 11. Dimensions of Anger Reactions
- 12. PROMIS Anxiety
- 13. PROMIS Depression

*NOTE: For time constraints, the urine test can be administered during the waiting period prior to the second cortisol sample.

AT THIS POINT, THE FIRST SALIVARY SAMPLE IS COLLECTED

14. Negative Life Events Inventory

15. PCL 5- *Worst life event* (this is the event that bothers them the most, from their entire life)
16. PCL 5 - *Recent (past year)* this is a traumatic event that has happened to them recently (in the past year) - it may or may not be the same as #16

17. Trauma Imagery Stress Task (the Negative Life Events Inventory and the PCL build up to this)

Subsection 2.9 - Phase II Brief Stress Task (Trauma Imagery Task)

After completing the PROMIS Depression, the participant will provide a saliva sample. They will then complete the negative life events inventory and the PCL 5 (for worst event in their life and a recent event). The reason that the saliva sample is taken before these measures and not directly before the Trauma Imagery Task is because in pilot studies the women began to

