become distressed when recounting their traumas during the Negative Life Events Inventory and the PCL; thus, the "baseline" for cortisol is now taken PRIOR to these items.

After completing the PCL for worst event and recent event, the participant will complete a a modified script-driven imagery task (Seo et al., 2013), derived from prior research with women with PTSD. Participants will be asked to recount a traumatic event via written response. The RA will provide a paper and pen and instruct the participant to recall the event exactly as it happened. The RA can offer prompts to recall sight, smell, and sound. The participant will then recount the event to the RA. Script driven imagery tasks have been effectively and safely used to assess traumatic-stress responses in individuals with PTSD. However, RAs will be highly trained to assess any severe distress that may arise and will immediately notify the PI and site clinical staff immediately. Responses will be subsequently destroyed. *AFTER THE COMPLETION OF THE TRAUMA IMAGERY TASK THE 20 MINUTE POST-SALIVA SAMPLE TIMER STARTS!* When the timer starts, the RA will not interact with the participant. They should sit quietly or may read.

Subsection 2.10 - Phase II Biospecimen Collection

Urine Collection: Participants will provide a urine sample to validate self-report drug use. A 5panel FDA-approved urine test cup will be used in this study. The participant will be instructed to urinate in the cup, close the cup, and then bring it back to the RA to read. Gloves will be used at all times and the RA should read the cup without touching it if possible. The participant will then be instructed to dispose of their urine in the restroom.

Saliva Collection: Before and twenty minutes after the brief stress task (Trauma Imagery Stress Task), women will be asked to provide a salivary sample. Women will be instructed to avoid eating, brushing teeth or smoking for one hour prior to the collection of saliva and will be asked to wait to begin the task if they have. Participants will passively drool into a collection vial for three minutes or until 0.80 milliliters of fluid is collected.

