Saliva samples will be immediately placed in the on-site freezer or cooler and be taken to IISBR or to [name] research lab for storage. Saliva samples will be transferred to IISBR within 36 hours to be frozen at -80°C until assayed. After the second and final collection, participants will be offered snacks and a drink and be debriefed using an IRB-approved script (see below).

Debriefing script:

Thanks so much for your participation. I know that might have been difficult for you to recall this event. I want to thank you and let you know that we think your participation in this task will help other women who have experienced adversity. While feeling a little distressed might be expected, we want to make sure you are not experiencing a lot of distress. Right now are you are experiencing a lot of distress?

If yes, ask if they want you to get a site staff from Prototypes/Serenity House AND contact the Principal Investigator, [name] [name] immediately AND provide [name] contact information to them).

If no, thank them for their time and remind them if anything comes up they can call the Principal Investigator, [name] [name] and/or talk to any of the Prototypes/Serenity House site staff. (Provide [name] contact information to them).

Provide water and snacks at this time and pay close attention to any noticeable changes in mood until they are released to the care of the Prototypes/Serenity House site staff. Immediately inform [name] AND Prototypes/Serenity House site staff of any potential issues.

Subsection 2.11 - Phase II Biospecimen Analysis

Urine Sample: The 5-panel FDA-approved urine test cup screens for metabolites of the following drugs of abuse at the established cut-off levels and is used for qualitative purposes: Amphetamines (1000 ng/mL), Cocaine (300 ng/mL), Methamphetamines/ MDMA (500 ng/mL), Opiates (2000 ng/mL), and THC (50 ng/mL). Urine sample validity checks will be provided by temperature and adulterant monitoring strips built into the test cup. Participants whose urine does not pass validity checks will be counted as positive for drugs. Results will be coded qualitatively (above or below threshold). All positive results will be interpreted as positive, regardless of self-report.

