- 1. Read participant consent to screen document (listed in Appendix)
- 2. If they agree to consent to screen, you will open the Screening Module in REDCap.
 - 1. Age? (Must be 18 or older)
 - 2. Able to speak English (infer, don't ask)
 - 3. Homeless in the last 6 months.
 - i. Homeless is defined as anyone who spent the previous night in a public or private shelter, or on the street. Some women will have been incarcerated. If this is the case and they did not have another residence to return to, they are eligible to be in the study.
 - 4. Administer Short Blessed Test.
 - i. Must meet (Normal Cognition 0-4)
 - 5. Meet likely subthreshold or threshold PTSD as measured by PCL-5 (see Appendix).
 - 6. Subthreshold PTSD
 - i. Must meet Criteria A (exposure to a traumatic event).
 - ii. Must endorse "moderately" or more to at least 2 B-E criteria. This will be automatically scored in REDCap.

Subsection 5.2 Informed Consent

- 1. If eligible, read to them the informed consent, going over key highlighted areas.
 - i. Provide them a paper copy of the consent, and highlight the contact information for [name] and the IRB.
 - ii. Download a copy of informed consent (save in downloads). Have them sign. Then re-upload and delete from downloads.
- 2. START locator guide.
 - i. Make sure you get their FULL LEGAL NAME!
 - ii. TAKE PICTURE USING THE "ADD DOCUMENT" ITEM, DO NOT SAVE TO CAMERA AND THEN UPLOAD.

Subsection 5.3 Baseline Protocol

 Tell them there will be a urine test. They can take it before or after interview (their choice). You will hand them a cup. They will return the cup and you will record their urine results in REDCap. Use gloves. It is not considered a biohazard so can be thrown in trash (or urine poured in toilet).

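### Section 2.9 makes the wait before the second cortisol sample a no-contact rest, but Section 2.8 lets the drug test be done in it, so the post-task interval is not standardised when that option is used

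*Combined protocol and SAP*

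**What the plan says.** Section 2.8 lists the baseline assessments in order. The urine drug test is item 1, the first saliva sample follows item 13, and the trauma imagery task is item 17. A note under the list adds: "For time constraints, the urine test can be administered during the waiting period prior to the second cortisol sample".

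Section 2.9 defines the wait: "AFTER THE COMPLETION OF THE TRAUMA IMAGERY TASK THE 20 MINUTE POST-SALIVA SAMPLE TIMER STARTS". It then sets the rule for it: "When the timer starts, the RA will not interact with the participant. They should sit quietly or may read". Urine is not mentioned as an exception.

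Section 2.10 describes the urine test: "The participant will be instructed to urinate in the cup, close the cup, and then bring it back to the RA to read". Section 5.3 tells staff something else about when to do it: "They can take it before or after interview (their choice". Section 2.2 lists urine ahead of the stress task.

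On distress, Section 2.9 also states that "RAs will be highly trained to assess any severe distress that may arise" and that the investigator and clinical staff are to be told at once. The scripted question, "Right now are you are experiencing a lot of distress", belongs to the debriefing in Section 2.10 and Appendix II, which follows the second sample.

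The SAP fits a random-intercept mixed model to each outcome, with group, time, their interaction and site. It does not define cortisol reactivity and does not mention urine timing. The combined file contains the protocol twice, with the same wording on these points in both copies.

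**The concern.** Cortisol reactivity compares a sample before the task with one after it, so what happens between the two samples is part of the measurement. The protocol treats the interval that way. It moved the first sample ahead of the trauma questionnaires because pilot participants became distressed during them. It confines saliva collection to 10am to 2pm, restricts food and smoking, and imposes a quiet rest. The note in Section 2.8 removes the last of these controls at some visits, according to time pressure.

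A drug test read by study staff in a residential drug treatment facility could plausibly be stressful in itself, and it adds walking and conversation. That is a judgement, since no passage says that the test alters cortisol. At stake is whether post-task samples from different women and visits were taken under the same conditions.

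A second, separate matter is that staff are told to assess severe distress and to act immediately, yet not to interact once the timer starts.

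**Working it through.** No sample size, power or alpha figure is involved. The check sets the passages side by side, with some simple timing arithmetic.

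**1. Is it the same wait?** The note refers to the wait before the second cortisol sample. The only such wait described is the 20-minute timer in Section 2.9. The two passages govern the same minutes.

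**2. Can both be followed?**

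| Place | Content | Fits a no-contact rest? |
|---|---|---|
| 2.8, list | Urine is item 1, before the first saliva sample | Yes |
| 2.8, note | Urine may be done in the wait | No |
| 2.9 | No contact with the RA; seated quietly or reading | This is the rule itself |
| 2.10 | Participant is instructed, provides urine, returns the cup to be read | No, if done in the wait |
| 5.3 | Before or after the interview, participant's choice | Depends on when it is done |

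The note is permissive. If urine is taken at position 1, or after the second sample, Section 2.9 can be followed. The conflict arises only when the optional slot is used.

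**3. Could a test in the wait register in the second sample?** Basic Definitions says that cortisol "is released in the body about 20 minutes after a stressor". A test begun t minutes into the wait leaves 20 − t minutes before the second sample:

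- t = 0: 20 − 0 = 20 minutes
- t = 5: 20 − 5 = 15 minutes
- t = 10: 20 − 10 = 10 minutes
- t = 15: 20 − 15 = 5 minutes

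On the protocol's own lag, only a test begun very early in the wait could start to show, and most of any response would come at or after the sample. The drool takes up to 3 minutes, which changes this little. Section 2.6 adds an uncertainty. The second sample is to be collected as the first was, and that procedure includes a 10-minute mouth rinse. If the rinse falls inside the wait, it is another activity there. If it follows the wait, collection starts at 20 + 10 = 30 minutes, and tests begun in the first 10 minutes would reach the 20-minute lag.

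**4. Which outcomes are exposed?** Both PCL-5 administrations are items 15 and 16, before the task at item 17, so urine in the wait cannot affect the primary outcome at that visit. The exposed outcome is cortisol reactivity. Salivary CRP is assayed from the same samples, but no CRP response time is given to judge it by.

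**5. Would the analysis absorb it?** The fixed site effect would take up a constant difference in level between sites. Arms alternate between sites by cohort, and the SAP has no cohort term, so a practice that changed from one cohort to the next could coincide with arm. The SAP's covariate screening could address this only if urine timing was recorded, and no timing field is described.

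**6. Distress during the wait.** The debrief question comes at least 20 minutes after the task ends, or 20 + 3 = 23 minutes with a full-length drool and no separate rinse. Before that, the Appendix II script invites the participant to report severe distress, and staff are told to stop the procedure if she is extremely distressed. No passage says how the no-contact rule and the duty to assess fit together during the wait.

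**The case against.** The best reply is that this is a wording conflict with little behind it. The note only allows the slot, the listed order puts urine first, and the cortisol lag means that most tests in the wait would come too late to matter. Much of that stands, and it rules out several stronger readings that a reader might infer:

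- **That cortisol reactivity is contaminated.** Nothing in the documents shows an effect of the test on cortisol, and the timing in step 3 limits it. What remains is an interval that is not the same for everyone.
- **That the arm comparison is biased.** That would need use of the slot to differ by arm. It is possible given allocation by site and cohort, but there is no evidence of it, and the site effect removes part of the risk.
- **That the instructions can never all be followed.** They can, whenever the optional slot is left unused.
- **That all task visits are affected.** The planned attendances in Section 2.16 sum to 134 + 120 + 96 = 350, but this is an inferred ceiling. The note sits in the pre-intervention section and is not repeated for follow-ups, some follow-ups may be remote, and samples may be refused. How often the slot was used is not given.
- **That nobody looks for distress before the debrief.** Not interacting is not the same as not observing, and the safeguards in Section 2.9 and Appendix II come earlier. The debrief holds the only scripted question about distress, but it is not the only safeguard.

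The objection does not remove the contradiction itself. Section 2.9 sets a condition for measuring a named outcome, Section 2.8 waives it for convenience, and nothing elsewhere settles which applies.

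**Conclusion.** The contradiction between Sections 2.8 and 2.9 is certain from the text, and Section 2.10 confirms that the test cannot be done under the Section 2.9 rule. Section 5.3 adds a further, looser instruction. When the slot is used, the post-task interval is not standardised, and this may add uncontrolled variation to cortisol reactivity. No size, direction or difference by arm can be derived from the documents, and the number of affected visits is unknown. The primary outcome is not touched. This is worth correcting because the remedy is cheap, not because harm to the result has been shown.

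The distress wording is a separate and narrower point: two instructions in Section 2.9 need reconciling for the 20 minutes of the wait.

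**What to change.** - Delete the note under the order of assessments in Section 2.8 and replace the open choice in Section 5.3.
- Set a single urine position outside the interval between the two saliva samples: position 1 of the existing order, at all three visits and both sites. Section 2.6 already allows procedures to start before 10am, so this need not use up the saliva window.
- Add a REDCap field for the time of urine collection.
- For completed visits, if timing can be recovered, count the urine-in-wait visits by arm, site and time point, and run a sensitivity analysis of cortisol reactivity without them. If it cannot be recovered, report this as a limitation. The SAP is written in the past tense, so this step may be the only one still open.
- Ask the clinical team to reconcile the no-contact rule in Section 2.9 with its text on assessing distress and notifying at once, so that staff know which governs during the wait. The content of that rule is theirs to decide.

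The cost is a few lines of protocol text, one data field and, where feasible, one extra analysis. Visits that would have used the wait for urine become a few minutes longer.

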- c. Tablets will be programmed by the Research Director from the School of Nursing and responses will be automatically, electronically scored. All participants who complete the screener will receive \$3.
 - i. Note: those who complete the screener must complete the consent to screen, but are not assigned a participant ID at this time as they have not completed the **Informed Consent**. As such it is imperative that accurate information be obtained with respect to the individual's name as that will be used to link it to their subsequent data.

- 2. Group Assignment and Intervention Procedure (may chance due to evolving circumstances due to COVID-19)
 - a. Prior to recruitment, the Residential Treatment Sites (RTS; Pomona and Escondido) will be randomized to receive the MBI or serve as the attention-control (HP); recruitment and research procedures (MBI or attention-control) will occur at both sites simultaneously. Women will live at sites prior to recruitment.
 - b. Informed consent there are TWO versions of the Informed Consent documents. One is for the MBSR course: the other is for the HP course. Women will complete ONE of the Informed Consent forms, depending on which group they are in. It is imperative that the correct form is filled out and uploaded onto REDCap.
 - c. Baseline questionnaire administered:
 - i. After informed consent, participants will complete a baseline questionnaire. In addition to the traumas indicated in the PCL-5, participants will report lifetime history of trauma (including whether events occurred in adulthood, childhood, or both).
 - ii. Questionnaire data will be collected via tablet and transferred to RedCap.
 - iii. Participants will provide a urine sample for a drug test to validate self-report. Then participants will complete the brief stress (Trauma task providing saliva samples both before and after the task.
 - d. Locator guide: this is a critical part of maintaining contact with our participants. However, they may not be inclined to provide all the information on the first or second meeting. PLEASE TAKE THE PICTURE AT THE TIME OF ADMINISTERING **INFORMED CONSENT.** The rest of the locator guide can be filled out over the course of the study. Given issues with COVID-19, we will start completing the Locator Guide after session 2 or 3. Please see PI or Lab Management Team for further guidance.
 - e. Intervention

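### The protocol gives conflicting orders for the urine test and the TCU self-report it is meant to validate, and neither masks the result nor records the order used

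*Combined protocol and SAP*

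**What the plan says.** The purpose of the test is stated in Section 2.2, "Participants will provide a urine sample for a drug test to validate self-report", and again in Section 2.10, "Participants will provide a urine sample to validate self-report drug use". Section 2.14 repeats it for the post-assessment.

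The order is described in three ways:

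- **Section 2.2** (Group Assignment and Intervention Procedure) has the baseline questionnaire first, then urine, then the stress task.
- **Section 2.8** (Order of assessments) has "1. Drug test (urine" followed by "2. TCU Drug Screen (self-report". A note below the list adds: "For time constraints, the urine test can be administered during the waiting period prior to the second cortisol sample".
- **Section 5.3** (Baseline Protocol) opens with "Tell them there will be a urine test" and continues "They can take it before or after interview (their choice".

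Under Section 2.10 the woman is to close the cup and "bring it back to the RA to read". Under Section 2.8 research staff read the response options to her, enter her answers and lock each measure when it is finished.

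Appendix IV lists the TCU as a secondary outcome scored 0 to 9. Its opening line names baseline and 6 months, and its last sentence names all three waves. Sections 2.2 and 2.14 mention urine at follow-up after the questionnaire but do not place it explicitly against the TCU. The SAP models each secondary outcome over T1 to T3 and does not mention test order. The protocol text appears twice in the file, with the same wording in these sections.

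**The concern.** A test can validate an answer only if the answer was given without knowledge of the test result. If the cup has been read before the TCU is asked, the woman may be answering a member of staff who already holds the result. Agreement between the two measures then partly reflects that knowledge.

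Letting the woman choose the order raises a second problem. The women are in residential drug treatment (Section 2.1), and Section 2.15 expects some to worry about who will learn their survey or urine results. In that setting the choice of order could depend on recent use, which is the quantity being measured. The conditions under which the TCU is answered would then vary between women for reasons tied to the outcome, and nothing in the data would show which order was used.

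At stake are the TCU as a secondary outcome and any statement that urine confirmed the self-report.

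**Working it through.** The documents give no figure to reproduce, so the check sets the sections side by side.

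| Section | Urine relative to the TCU |
|---|---|
| 2.2, baseline | After the questionnaire, before the stress task |
| 2.8, numbered list | Immediately before |
| 2.8, note | After every questionnaire and the stress task |
| 5.3, baseline | Before or after, chosen by the woman |
| 2.2 and 2.14, follow-ups | Mentioned after the questionnaire; no explicit order |

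1. **The order is not fixed.** Staff could follow any of the first four rows at baseline and comply with some part of the protocol.

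2. **Independence is not protected.** Combining Section 2.8 (item 1, then item 2), Section 2.10 (cup read when handed back) and Section 5.3 (the staff member who hands over the cup records the result), the natural reading of urine-first is that the result is known to staff before the TCU is asked. This is an inference: Section 2.8 does not say when the cup is read, and no section says that the woman is told the result. Equally, no section withholds the result, uses a different person for the interview, or asks for the order to be recorded.

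3. **What differs between the orders.** Section 5.3 has every woman told of the test, so knowing that it will happen is common to both orders. The difference is whether staff may already hold the result.

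4. **The saliva-wait slot clashes with Section 2.9.** Once the 20-minute timer starts, the RA is not to interact with the participant, who is to sit quietly or read. Handing over a cup, sending her to the restroom and reading the cup on return cannot be done under that rule.

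5. **What is not affected.** Sections 2.11 and Appendix IV count a positive urine result as positive whatever the woman reported, so the urine outcome does not depend on the order.

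**Illustration only.** Every rate here is an assumption. Let p be the share of women who would test positive, and g the gain in disclosure when staff already have the result. Assume no false reports of use. The shift in reported use from order alone is p × g.

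- With p = 20% and disclosure of 60% (TCU first) or 90% (urine first), reported use is 0.20 × 0.60 = 12% or 0.20 × 0.90 = 18%, a shift of 6 points.
- Over p = 10% to 40% and g = 10 to 30 points, the shift runs from 0.10 × 0.10 = 1 point to 0.40 × 0.30 = 12 points.
- If the share tested first differed by 30 points between two groups, the spurious difference is 0.30 times the shift: 1.8 points for the single case, with a range of 0.3 to 3.6 points. Nothing in the documents indicates such an imbalance.
- For scale, 1.8% of the 67 women per arm in Section 2.5 is 1.2 women. At 15% prevalence the simple standard error of a between-arm difference is √(2 × 0.15 × 0.85 / 67) ≈ 0.062, about 6 points.

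These figures concern any reported use. They do not translate directly to the 0 to 9 TCU score that Appendix IV describes.

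**The case against.** Three stronger readings are tempting, and the documents support none of them.

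- **That Section 2.8 always has the cup read before the self-report.** Its own note permits urine after all the questionnaires, and Section 2.2 puts the questionnaire first.
- **That the bias varies by visit and by arm.** Section 5.3 covers baseline only, and the follow-up order is unspecified rather than stated to differ. Both arms follow the same visit script. Because arm is assigned by site within cohort, local habits could line up with arm in a given cohort, but nothing shows that they do.
- **That women who have used can escape checking by being asked first.** Urine is due in either order and a positive stands regardless. Interview-first is in fact the independent order.

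The best remaining argument is that fixing urine last has a price. On the illustrative figures, reported use would be 12% with urine last and 18% with urine first, against 20% true use, so the independent order gives the less complete self-report. Advance notice does not remove that difference, since it is already given to everyone. The SAP also plans no analysis of agreement between urine and self-report, so inflated agreement would not reach a planned result.

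The trade-off is real and should be acknowledged. It does not support leaving the order open, because a mixture of unrecorded orders gives neither a clean validation nor a consistently measured outcome. The absence of a planned agreement analysis narrows the consequence, but the protocol still gives validation as the reason for the test and the TCU is still modelled as an outcome.

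**Conclusion.** The inconsistency is established from the text: Sections 2.2, 2.8 with its note, and 5.3 cannot all be followed, and the slot in the note conflicts with Section 2.9. It also follows from the text that the test may be read before the answer it is meant to validate, with no safeguard and no record of order.

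Bias in the TCU is possible but not shown. It rests on two assumptions: that disclosure changes when staff may already know the result, and that order differs between women or waves in a way related to use. The documents give no urine positivity, disclosure rate or share tested first, so neither size nor direction can be derived from them. The primary outcome is not involved. The change is worth making because it is cheap and removes a self-selected source of variation from a named secondary outcome.

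**What to change.** Reconcile Sections 2.2, 2.8 (list and note), 5.3 and 2.14, in both copies of the protocol text, to one order for every woman at all three waves:

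1. Tell her that a urine test will follow, as Section 5.3 already does.
2. Complete and lock the TCU, using the existing locking step.
3. Only then hand over the cup, at one fixed point outside the wait before the second saliva sample.

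Delete the clause in Section 5.3 that leaves the order to the woman, move item 1 of the Section 2.8 list accordingly, and remove the note. Add one REDCap field for the order actually used.

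No new procedure is needed. The costs are the scheduling flexibility that the note was written to provide, and possibly somewhat lower disclosure than if the result were already known.

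The SAP is written in the past tense. If collection is complete, report the order used wherever it can be recovered, check whether the TCU results are sensitive to it, and do not present urine and self-report agreement as independent validation.
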